2.2. Specific goals

- a. - Estimating Hyperkalaemia prevalence in these patients.
- b. - Assessing the role of hyperkalaemia with the use of non-optimal therapy doses.
- c. - Estimating 12 months hyperkalaemia incidence on these patients and describing the severity of the episodes.
- d. - Estimating incidence of HF hospital admission and/or death in these patients on a medium term basis (12 months) and its association with existence of hyperkalaemia during follow up.
- e. - Assessing hyperkalaemia risk during follow-up in relation with the existence of diabetes and/or renal failure (RF) at baseline visit.

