3. STUDY DESIGN

National multicentric prospective observational study that includes 12 months follow-up of consecutive cases of HF outpatients with REF. Inclusion baseline visit and follow-up visit at 12 months will be scheduled for collecting clinical and blood sample data of patients indicated later on in this protocol.

The study will be performed in ordinary conditions of clinical practice; no additional procedures or interventions will be performed. Patients will be selected in cardiology outpatient clinics of 20 Spanish centres, including the first 30 patients meeting inclusion and exclusion criteria. All patients will undergo the common studies according to usual clinical practice and at least both, potassium and renal creatinine clearance values will be collected.

To respond to the main objective, prevalence of hyperkalaemia (as defined later in the protocol) at baseline will be determined as well as the appearance of new hyperkalaemia cases in the follow up of patients that had normal potassium levels at baseline visit; their relationship with outcomes of interest will also be determined.

Variables to be collected at each visit are indicated in appendix 1.

3. 1. Definition of the study population and selection criteria

The study population is composed of HF outpatients with REF from excellence Spanish centres.

The study will be performed in 20 Spanish centres, either SEC HF- excellence certified, integrating official research networks or with excellent performance proven in previous similar initiatives (relation of centres and researchers in Appendix 2).

Every centre will include the first 30 consecutive cardiology outpatients who fulfil the inclusion criteria and that do not present any exclusion criteria. All pre-screened patients will be indicated, together with the reason of their exemption if occurs.

Inclusion criteria

1. Patients, women or men, aged 18 or more
2. Documented HF with REF (<40%) diagnosis
3. Signed written informed consent

Exclusion criteria

1. Any type of disorder affecting the capacity to give free and informed written consent
2. Clinical trial enrolment at the moment of the inclusion
3. Patients suffering stage 5 chronic kidney disease
4. Patients with less than a year life span due to diseases different from HF

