5. Not having completed HF drug titration stage at the moment of inclusion (this stage is not completed if, on doctor's judgement, possible maximum doses have not been reached in RAA system drugs and any of these drugs has been included or dose-modified in recruitment visit)
6. Informed consent refusal

At any time during follow-up patients can leave the study (and will be censored in the analysis) or retire their consent (and will be excluded from the analysis).

3. 2. Considerations about simple size

Assuming a 10% risk of outcomes (mortality or HF hospital admission) among the exposed (hyperkalaemia), 2.5% among the non-exposed and a 7:1 non-exposed/exposed ratio, 73 exposed and 511 non-exposed patients should be included to have a 80% power to detect these differences with a 95% confidence level. The recruitment goal is set at 600 patients.

This sample size allows a precision of $\pm 2,4\%$, assuming a prevalence of hyperkalaemia at baseline of 10% and with a 95% confidence level. Furthermore, assuming 5% hyperkalaemia cumulative incidence through follow-up among hyperkalaemia-free patients at baseline, the proposed sample size, allows a precision of $\pm 1,8\%$ with a 95% confidence level.

3. 3. Selection of centres

The number of participant centres throughout Spain will be 20 and a cardiologist will be the principal investigator at every centre. The centres have been selected either among those with excellence-certified HF units, included in CiberCV Consortium or

with good performance in previous similar registries; this selection is not random, but based on interest and high performance criteria in the field of HF.

3. 4.- Source of information

Data will be obtained directly from the participants at the planned visits and completed with the review of their medical records if needed.

3. 5. Variables and CRF (appendix 1)

The main outcome variables are:

a.- Hyperkalaemia. Serum Potassium (K^+) will be measured in baseline and follow-up visits, but also if there is any intermediate hospital admission. All available potassium measurements during follow-up will be reviewed and values of hyperkalaemia identified. Hyperkalaemia will be considered with (K^+) Values $> 5,4$ mEq/L

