6. PLAN FOR DATA ANALYSIS

Hyperkalaemia prevalence at basal visit and the rate of patients who do not receive and/or reach optimal doses of drugs of interest (ACIEs, ARB-II, MRAs) will be estimated and their corresponding 95% confidence intervals computed. The reason for not receiving and/or reaching optimal doses of drugs will be described, especially if it is due to hyperkalaemia.

For those patients who do not present hyperkalaemia at baseline, 12 month hyperkalaemia cumulative incidence (95% confidence interval) will be estimated; also it will be estimated the proportion of patients who have to modify their therapy due to hyperkalaemia.

The number of episodes of hyperkalaemia during follow-up in relation to the number of patients will be estimated and their severity and the therapy changes that induced described. Also 12 months cumulative incidence of clinical outcomes will be estimated: hospitalisation due to HF or to, hyperkalaemia (and related events) and mortality, considered as individual and composite outcomes. The association between hyperkalaemia and occurrence of outcomes will be analysed and also adjusted using potential confounding factors by means of logistic regression models

The quantitative variables will be generally described using either the mean and the standard deviation or the median and interquartile range according them following or not a normal distribution. When comparing groups, t-student test will be used for continuous variables and chi-square test for qualitative ones.

Both, intermediate and final analysis, are planned to be carried out after baseline-visit closure and at the end of follow up (12 months).

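### The 7:1 ratio behind the 80% power does not follow from the 10% prevalence and 5% incidence assumed in the same section; those rates give 84% power for baseline or new hyperkalaemia and 76% for baseline hyperkalaemia

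*Protocol*

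**What the plan says.** Section 3.2 of the Protocol has two paragraphs of figures for the same cohort.

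- **Power.** The risks are given as "Assuming a 10% risk of outcomes (mortality or HF hospital admission) among the exposed (hyperkalaemia), 2.5% among the non-exposed". The group sizes follow: "a 7:1 non-exposed/exposed ratio, 73 exposed and 511 non-exposed patients should be included to have a 80% power to detect these differences". Recruitment is then set at 600. No source is given for the 7:1 ratio.
- **Precision.** One half-width is computed "assuming a prevalence of hyperkalaemia at baseline of 10% and with a 95% confidence level", giving ±2.4%. The other is computed "assuming 5% hyperkalaemia cumulative incidence through follow-up among hyperkalaemia-free patients at baseline", giving ±1.8%.

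The exposure is described differently in different places. In Section 2.2, goal d concerns the 12-month outcomes and "its association with existence of hyperkalaemia during follow up". Section 3 names baseline prevalence together with new cases among patients with normal potassium at baseline, and adds that "their relationship with outcomes of interest will also be determined". Section 6 says only: "The association between hyperkalaemia and occurrence of outcomes will be analysed".

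**The concern.** A 7:1 ratio is a statement about how common the exposure is: one patient in eight. The following paragraph makes its own statement about how common hyperkalaemia is, at baseline and during follow-up, in the same 600 patients. The two should agree, or the protocol should say why they differ. They do not agree, and no reason is given.

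The 80% is the only assurance offered for the association between hyperkalaemia and death or heart failure admission, which is part of the main goal. If the exposed group is smaller than 7:1 implies, a null association would be read against a power that the study did not have. If it is larger, the protocol understates its own power.

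**Working it through.** **Inputs, all from Section 3.2.** Outcome risk p1 = 0.10 in the exposed and p0 = 0.025 in the non-exposed; ratio k = 7; power 80%; 95% confidence, taken as two-sided 5% because that reproduces the stated sizes; N = 600; baseline prevalence 10%; incidence 5% among patients free at baseline.

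**1. Reproduce the stated sizes.** Two proportions, pooled variance under the null, no continuity correction:

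n(exposed) = [1.96·√((1 + 1/k)·p̄(1 − p̄)) + 0.8416·√(p1(1 − p1) + p0(1 − p0)/k)]² / (p1 − p0)²

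With p̄ = (0.10 + 7 × 0.025)/8 = 0.0344, this is (0.3817 + 0.2573)² / 0.075² = 72.6, so 73 exposed and 7 × 73 = 511 non-exposed. Power at 73:511 is 80.2%. The stated figures are right for their inputs.

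**2. Exposed patients implied by the 10% and 5%.**

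- Baseline cases: 0.10 × 600 = 60, leaving 540 free.
- New cases: 0.05 × 540 = 27.
- Baseline exposure: 60:540 = 9:1.
- Baseline or new: 60 + 27 = 87, so 87:513 = 5.9:1.
- For 7:1 to come from pooling with 10% prevalence, incidence would have to be (0.125 − 0.10)/0.90 = 2.8%, not 5%.

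**3. Power for those splits.** Power = Φ[(0.075 − 1.96·s0)/s1], where s0 = √(p̄(1 − p̄)(1/e + 1/n)), s1 = √(p1(1 − p1)/e + p0(1 − p0)/n), and p̄ is the overall risk for e exposed and n non-exposed.

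- 60:540: s0 = 0.02413, s1 = 0.03931, giving Φ(0.705) = 76.0%.
- 87:513: s0 = 0.02156, s1 = 0.03289, giving Φ(0.995) = 84.0%. Both stated group sizes are also met, since 87 exceeds 73 and 513 exceeds 511.
- 75:525 (7:1 in 600), for comparison: 80.9%.

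**4. Goal d read literally.** If exposure is any hyperkalaemia during follow-up, the exposed are the 27 new cases plus the share f of the 60 baseline cases that are hyperkalaemic again. The protocol gives no f, so the values below are assumptions that show the range.

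| f (share of 60) | Exposed:non-exposed | Power |
|---|---|---|
| 0% | 27:573 | 57% |
| 25% | 42:558 | 68% |
| 50% | 57:543 | 75% |
| 75% | 72:528 | 80% |
| 100% | 87:513 | 84% |

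The threshold for 80% in 600 patients is 72 exposed (80.06%; 71 gives 79.75%), so 72 − 27 = 45 of 60 must recur. An exact 7:1 split (75:525) needs 75 − 27 = 48 of 60.

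**5. Check on the approximation.** Exact binomial enumeration of the uncorrected chi-square test gives 81.8% (73:511), 76.3% (60:540), 85.3% (87:513), 75.2% (57:543) and 54.1% (27:573). The last split has only 27 × 0.10 = 2.7 expected exposed events, so its normal-theory figure is rough.

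**6. Size on the risk scale.** Against 2.5% in the non-exposed, the exposed risk detectable with 80% power is 9.4% at 87:513, 10.7% at 60:540, 10.9% at 57:543 and 15.0% at 27:573.

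**The case against.** The sample-size calculation contains no arithmetic error, and both stated precisions reproduce. The two paragraphs serve different purposes, and the protocol does not claim that the ratio was derived from the rates. Section 3 supports counting baseline and new cases together, and on that reading 80% is met with margin. On the baseline reading the loss is four points of power, and the detectable risk moves only from 10% to 10.7%. The choice of exposure for the association model may also properly be left to the SAP.

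Most of this stands and limits the point. It does not remove it: both paragraphs describe the same 600 patients, and the protocol already commits to a ratio, group sizes and a power that its own rates do not produce. Correcting a stated figure is different from asking for detail that an SAP may hold.

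Two stronger readings are tempting and are not supported.

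- *That 7:1 is impossible under the protocol's rates.* Under goal d's wording it arises if about 48 of the 60 baseline cases are hyperkalaemic again. The fault is that this share is nowhere stated.
- *That the study has only 57% power for goal d.* This needs every baseline case to stay free of hyperkalaemia for 12 months and to be counted as non-exposed. Goal d refers to the existence of hyperkalaemia, not to new cases only, and Section 3.5 provides that "All available potassium measurements during follow-up will be reviewed and values of hyperkalaemia identified", so recurrences in baseline cases would be found and counted.

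**Conclusion.** The point holds as a minor correction of a stated design figure. The 7:1 ratio in Section 3.2 does not follow from the 10% and 5% in the next paragraph. Whether the 80% is safe depends on the exposure meant: it is conservative if baseline and new cases are pooled, slightly short for baseline exposure, and undetermined on goal d's literal wording until a recurrence share is given.

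This rests on the protocol's own risks of 10% and 2.5%, a two-sided 5% test without continuity correction, and all 600 patients being analysed. With 584 analysed, power would be about 75% for baseline exposure and 83% pooled, so the conclusion does not change. The sample size itself is not in question.

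**What to change.** Keep 600 patients and edit Section 3.2 only:

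- State which hyperkalaemia is the exposure for goal d.
- Replace 7:1 with the ratio implied by the 10% and 5% for that exposure, and restate the power: 87:513 with about 84% for baseline or follow-up hyperkalaemia, or 60:540 with about 76% for baseline hyperkalaemia.
- If only hyperkalaemia during follow-up counts, state the assumed share of baseline cases that are hyperkalaemic again and the power it gives. The 7:1 ratio can then stay only if that share is about 80% (48 of 60).

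The cost is a few sentences. No patients, visits or data items are added, although the stated power may become less favourable.

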1. BACKGROUND AND RATIONALE

In the last years, multiple reasons have been increasing the disease burden of heart failure (HF) in industrialised countries – also Spain –, being a very important health problem. It is foreseeable that this burden will continue increasing in our country¹.

In parallel with this evolution, several treatments already included in clinical practice guidelines^{2, 3}, have proved to be effective in selected groups of patients, especially those with systolic function impairment.

These treatments that interfere with the renin-angiotensin-aldosterone system, increase hyperkalaemia risk in HF patients as much as three times^{3, 4}. Hyperkalaemia is associated with conduction disorders and risk of potentially life-threatening arrhythmias; it is not rare at all, as 20 years ago estimations already indicated 1-10% prevalence in hospitalised patients⁵. More recent data among ACEI new users suggest in the first year 5,6% and 1,7% for potassium values >5 and >5,5 respectively.⁶ HF patients are at increased risk of hyperkalaemia, not only due to the drugs they receive (ACEIs/ARB-II, mineralocorticoids receptor antagonists (MRAs) and, more recently, sacubitril/valsartan), but also because of the frequent presence of comorbidities (diabetes or renal failure, among others).⁷

These drugs blocking the renin-angiotensin-aldosterone system have an IA indication in the clinical practice guidelines for patients with reduced ejection fraction, so their use is becoming more frequent and, subsequently, hyperkalaemia is a growing concern for treating HF patients.⁷

Despite the above mentioned, there is no evidence of prospective information for the estimation of hyperkalaemia problem in HF patients in the daily Spanish clinical practice, although some current registries allows an initial estimation of its prevalence. In a recent analysis of the patients included in Spain in the Heart Failure Registry of the European Society of Cardiology (ESC)⁸ 26,3% of patients (401/1526) where MRAs are indicated (REF), but not prescribed, the underlying reason for not prescription is Hyperkalaemia in 8,5% of them (34/401). There are many “not-prescriptions” that are not adequately justified, therefore hyperkalaemia has a larger prevalence (30,6%, 34/111) among cases where a cause for avoiding MRAs does exist. At least as important is the fact that the vast majority of patients, up to 3 of 4, do not reach the

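### The stated precision of ±2.4 and ±1.8 points holds only with no within-centre correlation, an assumption Section 3.2 does not state for a sample of 30 patients at each of 20 centres

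*Protocol*

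**What the plan says.** Prevalence and 12-month incidence of hyperkalaemia come first in the main goal (Protocol, Section 2.1). Section 3.2 sets the size ("The recruitment goal is set at 600 patients") and then says what precision this allows: ±2.4 points "assuming a prevalence of hyperkalaemia at baseline of 10% and with a 95% confidence level", and ±1.8 points for a 5% cumulative incidence among patients free of hyperkalaemia at baseline. It mentions neither an intra-centre correlation nor a design effect.

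The sampling is fixed elsewhere in Section 3. Section 3.3: "The number of participant centres throughout Spain will be 20". Section 3.1: "Every centre will include the first 30 consecutive cardiology outpatients who fulfil the inclusion criteria". On how the centres were chosen, Section 3.3 says that "this selection is not random, but based on interest and high performance criteria in the field of HF".

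Section 6 says that prevalence and the rates of non-optimal treatment "will be estimated and their corresponding 95% confidence intervals computed", and it also plans a 95% interval for cumulative incidence. It names no interval or variance method.

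On the target, Section 3.1 says: "The study population is composed of HF outpatients with REF from excellence Spanish centres". Section 1 motivates the registry by the lack of prospective information for the "estimation of hyperkalaemia problem in HF patients in the daily Spanish clinical practice".

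**The concern.** Patients from one clinic tend to resemble each other more than patients from different clinics. If they do here, 600 patients in 20 groups of 30 carry less information about a wider population than 600 independent patients, and the precision in Section 3.2 is too favourable.

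The protocol gives reasons to expect some correlation:

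- Testing follows each centre's usual practice (Section 3), and the text describes no central laboratory.
- Incident cases are found by reviewing whatever potassium values exist (Section 3.5). How often a centre tests therefore affects how many cases it finds. Section 3.7 accepts that mild rises between visits may be missed.
- Whether titration is complete, and hence eligibility, is left to the physician's judgement (Section 3.1, exclusion criterion 5).
- Centres enter by different routes: certified units, a research consortium, or past registry performance (Section 3.3).

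The figures at stake describe how precisely the study can answer its main goal. A later analysis plan could choose a suitable interval, but it would not correct this planning statement.

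**Working it through.** **Inputs.** From the protocol: N = 600; 20 centres with 30 patients each; prevalence p = 0.10; cumulative incidence p = 0.05; 95% confidence. Derived: 600 × 0.90 = 540 patients free of hyperkalaemia at baseline, or 540 / 20 = 27 per centre on average. Assumed, because the protocol gives none: ICC 0.01, 0.02 and 0.05.

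**Step 1. Reproduce the stated figures.** Half-width = 1.96 × √(p(1 − p)/n).

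- Prevalence: 1.96 × √(0.10 × 0.90 / 600) = 1.96 × 0.01225 = 2.40 points. Stated: ±2.4.
- Incidence: 1.96 × √(0.05 × 0.95 / 540) = 1.96 × 0.00938 = 1.84 points. Stated: ±1.8. With n = 600 the result would be 1.74, which rounds to 1.7, so the stated figure fits the 540.

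Both figures match, so the design effect used is 1.

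**Step 2. Allow for centre.** Design effect DE = 1 + (m − 1) × ICC, with m = 30 for prevalence and m = 27 for incidence. Half-width = c × √(DE × p(1 − p)/n), with c = 1.96 (z) or c = 2.093 (t with 20 − 1 = 19 degrees of freedom). Effective n = n / DE.

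| ICC (assumed) | DE, m = 30 | Prevalence, z | Prevalence, t19 | Effective n | DE, m = 27 | Incidence, z | Incidence, t19 | Effective n |
|---|---|---|---|---|---|---|---|---|
| 0 | 1.00 | ±2.40 | ±2.56 | 600 | 1.00 | ±1.84 | ±1.96 | 540 |
| 0.01 | 1.29 | ±2.73 | ±2.91 | 465 | 1.26 | ±2.06 | ±2.20 | 429 |
| 0.02 | 1.58 | ±3.02 | ±3.22 | 380 | 1.52 | ±2.27 | ±2.42 | 355 |
| 0.05 | 2.45 | ±3.76 | ±4.01 | 245 | 2.30 | ±2.79 | ±2.98 | 235 |

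The z and t columns must not be mixed. If the analysis uses t on 19 degrees of freedom, the planning range for prevalence over ICC 0.01 to 0.05 is ±2.9 to ±4.0, not ±2.7 to ±3.8.

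**Step 3. How much correlation is needed?** The half-width rounds above the stated figure once it passes 2.45 (prevalence) or 1.85 (incidence).

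- Prevalence: ((2.45 / 2.4005)² − 1) / 29 ≈ 0.0014.
- Incidence: ((1.85 / 1.8382)² − 1) / 26 ≈ 0.0005.

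**Step 4. Coverage if an interval took no account of centre.** Approximate coverage is 2Φ(1.96 / √DE) − 1. For ICC 0.01, 0.02 and 0.05 this gives 92%, 88% and 79% for prevalence, and 92%, 89% and 80% for incidence. This shows what would follow from such an interval, not what the protocol plans.

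**The case against.** **The arithmetic is right.** This stands. Both figures are correct under independence, and the fault is an unstated assumption rather than a miscalculation.

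**The 20 centres can be treated as fixed strata.** Section 3.1 describes the population as patients of excellence centres, the sentence on daily Spanish practice is background rather than a listed goal, and Section 3.3 is open about the non-random choice. If inference stopped at these 20 clinics, no inflation would be needed, and with equal numbers per centre a stratified variance would be no larger than the simple-random-sample one. That is correct as a conditional statement, but no section limits inference in this way. Section 1 proposes the registry to fill a national evidence gap. Section 3.1 refers to excellence centres as a class, and Section 3.3 describes the 20 as selected from wider groups.

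**A design effect treats hand-picked centres as a random draw.** This stands as a limit on the remedy. A wider interval reflects variation between centres like these. It cannot make them representative of Spanish practice.

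**Little depends on the figures.** The target of 600 follows from the outcome comparison (73 + 511 = 584 patients), and no decision threshold rests on the precision. This is why no change in sample size is called for. Still, the figures are the protocol's only statement of how precisely prevalence and incidence will be estimated.

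**Two stronger readings are not supported.** A reader might infer that the planned 95% intervals ignore centre. Section 6 names no method, so it neither states nor excludes an allowance, and the statistical analysis plan, which is not at hand, may set it. A reader might also infer that the standard errors of the logistic models are too small by the same factor. Hyperkalaemia is a patient-level exposure that varies within centres, so the inflation for a single proportion does not carry over to its odds ratio, and the confounders are not named and could include centre.

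**Conclusion.** The point holds for Section 3.2. The stated ±2.4 and ±1.8 points assume no within-centre correlation without saying so, in a design that samples by centre and does not confine its conclusions to the centres sampled. Any ICC above about 0.0014 (prevalence) or 0.0005 (incidence) takes the half-width past the stated rounding.

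The size is conditional. With z = 1.96, the prevalence half-width is wider by about 14% at ICC 0.01 (√1.29 = 1.14) and 57% at ICC 0.05 (√2.45 = 1.57), with no widening at ICC 0. The ICC range is an assumption. The calculation also assumes equal centre sizes, full recruitment and complete follow-up of the 540. The protocol should be corrected on this point, but the recruitment target is unaffected.

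**What to change.** **Section 3.2.** State that ±2.4 and ±1.8 assume no within-centre correlation, and give the precision as a range over stated ICCs, using the same reference distribution as the analysis. Example: allowing for 20 centres, with an assumed ICC of 0.01 to 0.05 and a t reference on 19 degrees of freedom, the half-width is about ±2.9 to ±4.0 points for a prevalence of 10% and ±2.2 to ±3.0 points for a cumulative incidence of 5% in about 540 patients.

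**Section 6.** Specify that the intervals for prevalence and cumulative incidence use a cluster-robust variance with centre as the cluster and t on 19 degrees of freedom. This keeps the estimate as the marginal proportion; a random-intercept logistic model would give a centre-conditional value unless it was averaged over centres. If the statistical analysis plan already sets such a method, a cross-reference is enough.

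**Cost.** Wording in two sections and one analysis option. Patients are enrolled by centre, so no new data and no extra patients are needed. The price is a less favourable stated precision and somewhat wider intervals. The non-random choice of centres remains and should be reported as a separate limit on generalisability, for example in Section 3.7.

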b.- Proportion of patients using drugs with proven efficacy for HF with REF -but also linked with hyperkalaemia- (ACEIs/ARB-II/ARNI and MRAs) and proportion of patients with use of optimal doses (based on current ESC heart failure guidelines²) of the same drugs; reason for not using them (or not receiving optimal doses) will be registered.

Proportion of patients in the following categories will also be computed:

- No ACEi/ARB/ARNI or at less than target dose and no MRA
- ACEi/ARB/ARNI at target dose and no MRA
- ACEi/ARB/ARNI at target dose and MRA at less than target dose
- ACEi/ARB/ARNI at target dose and MRA at target dose

c.- Hospital admissions during follow-up and main cause for them. Outcomes considered will include HF admissions caused by hyperkalaemia and related events. Outcome Serum (K^+) values will be also registered.

d.- Mortality and cause.

HF (and hyperkalaemia) hospital admissions and mortality will be independently considered as outcomes; joint outcome incidence of both will be also calculated.

The remaining variables are set out in appendix 1. The most important variables are defined in section 4.

3. 6. Study development

Every participating centre will include from inclusion date (as described in section 3.1) the first 30 heart failure outpatients who fulfil the inclusion criteria and none of the exclusion ones. The excluded patients will be also registered, pointing out the reason of exclusion. The data to be collected during the initial visit will include the variables described in Appendix 1: demographic, clinical, blood sample test, and functional. A follow-up and final visit will be scheduled after 12 months for collecting all the variables the study requires (Appendix 1). Hospitalisation data since inclusion visit will be also collected, together with the information of blood sample test performed in such period for detecting hyperkalaemia episodes. Mortality data will include date and cause, where possible. If follow-up visit cannot be conducted, the reason for it will be registered. The collection and management of data is described in section 5. The envisaged length of the study is 24 months since approval date.

3. 7. Limitations

Mild elevations of serum potassium that do not lead to hospital admission between planned visits may go unnoticed.

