4. DEFINITION OF VARIABLES OF INTEREST

Heart Failure (HF) with reduced ejection fraction (REF): Patients with confirmed diagnosis of HF and with ejection fraction <40%.

Hyperkalaemia: K^+ values > 5,4 mEq/L.

Optimal doses: the maximum doses of renin-angiotensin-aldosterone related drugs that, according to the physician's judgement, the patient can receive. If any of these drugs (ACIEs, ARB-II, MRAs or sacubitril-valsartan) is *de novo* introduced at the initial visit, optimal doses will be not considered established.

A previous personal history of diseases and/or outcomes will be registered according to the usual practice of every centre. Some of the clarifications needed in every case are indicated as follows:

- **Coronary artery disease.** Documented existence of any of the following: acute myocardial infarction (AMI), acute coronary syndrome (ACS), coronary revascularisation (Percutaneous Coronary Angioplasty –PCA - or CABG) or coronary stenosis > 50% of arterial lumen in imaging test.
- **Cerebrovascular diseases.** History of ischaemic/haemorrhagic stroke or carotid stenosis > 50% of arterial lumen in imaging test.
- **Peripheral artery disease.** Aneurysm of thoracic/abdominal aorta or lower limb peripheral arterial disease.
- **Death due to a major cardiovascular event.** Due to ACS, HF, arrhythmia (sudden death), arterial aneurysm rupture or stroke.
- **Arterial thromboembolism.** Embolism phenomenon affecting arterial territory – (except pulmonary territory).
- **Ischaemic stroke.** Focal neurological deficit originated by cerebral ischemia; persists more than 24 hours after a sudden onset.

- **Haemorrhagic stroke:** Focal neurological deficit with sudden onset and originated by intracranial haemorrhage.
- **Acute coronary syndrome (ACS):** Acute coronary event that present typical ECG alterations and/or enzyme elevation.
- **NYHA functional class:**

Functional class I	No limitation. Ordinary physical activity does not cause dyspnoea, fatigue or palpitations.
Functional class II	Light limitation of physical activity. Everyday activities cause dyspnoea, fatigue or palpitations
Functional class III	Moderate limitation of physical activity. Activities considered less intense that everyday ones cause dyspnoea, fatigue or palpitations. Patient, however, does not present resting dyspnoea.
Functional class IV	Inability to perform activities without limitations. Symptoms may be present even at rest

- **Anaemia**

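### Goal d: the outcome admission itself adds potassium tests that count as exposure, so hyperkalaemia and admission are associated even with no true effect

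*Protocol*

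**What the plan says.** Section 3.5 (outcome a) has serum potassium measured at the baseline and follow-up visits, "but also if there is any intermediate hospital admission", and adds: "All available potassium measurements during follow-up will be reviewed and values of hyperkalaemia identified". Section 3.6 likewise collects hospitalisation data "together with the information of blood sample test performed in such period for detecting hyperkalaemia episodes". Section 4 defines hyperkalaemia as "values > 5,4 mEq/L", with no confirmation or time-window rule.

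Only one post-baseline visit is planned: "A follow-up and final visit will be scheduled after 12 months for collecting all the variables the study requires". Everything between the visits is usual care, since Section 3 states that "no additional procedures or interventions will be performed".

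Two specific goals in Section 2.2 use the resulting follow-up classification. Goal d links hyperkalaemia arising in follow-up to HF admission and/or death over 12 months. Goal e is: "Assessing hyperkalaemia risk during follow-up in relation with the existence of diabetes and/or renal failure (RF) at baseline visit". Section 6 analyses the link with outcomes by logistic regression, adjusted for potential confounders that it does not list. It sets no time order between the potassium value and the outcome.

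Section 3.7 gives one limitation: "Mild elevations of serum potassium that do not lead to hospital admission between planned visits may go unnoticed".

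**The concern.** When a case is anyone with at least one high value among all available tests, the chance of being a case rises with the number of tests. In goal d the number of tests depends on the outcome, because an admission brings a potassium measurement with it and that measurement counts towards exposure. The same rule lets a high value at the 12-month visit count as exposure for an admission that happened months earlier. A logistic model with a yes/no exposure and a yes/no outcome cannot tell these orders apart.

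At stake is the association between hyperkalaemia and outcome, which also drives the sample size in Section 3.2. Goal e could suffer in a similar way if the groups compared are tested at different rates.

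**Working it through.** **The plan's own figures.** Section 3.2 assumes outcome risks of 10% and 2.5%, a 7:1 ratio, 80% power and 95% confidence. The pooled risk is (0.10 + 7 × 0.025)/8 = 0.0344. Then n exposed = [1.96·√(0.0344 × 0.9656 × 8/7) + 0.842·√(0.10 × 0.90 + 0.025 × 0.975/7)]² / 0.075² = 72.6, so 73, and 7 × 73 = 511 non-exposed. The precision figures are 1.96·√(0.10 × 0.90/600) = 2.4% and 1.96·√(0.05 × 0.95/540) = 1.8%. All agree with the protocol, so the point does not rest on an arithmetic error.

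**Goal d under no true association.** Let every patient have m follow-up tests, and let a patient with the outcome admission have k more. The per-test chance p of a value above 5.4 is the same for everyone. With independent tests, P(classed as hyperkalaemic) is b = 1 − (1 − p)^m without the outcome and a = 1 − (1 − p)^(m+k) with it. For correlated tests, a normal random-intercept model with the same p and intraclass correlation (ICC) up to 0.7 replaces these formulas.

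The protocol does not give m, k, p or the ICC. The assumptions are m = 1-2, k = 1 or 3, p = 2-5% and ICC 0-0.7. The overall outcome risk r = 0.0344 comes from Section 3.2 as above. The quantity goal d would report is

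RR = [ra/(ra + (1 − r)b)] ÷ [r(1 − a)/(r(1 − a) + (1 − r)(1 − b))].

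Example with m = 1, k = 1, p = 0.05, ICC 0: b = 0.0500 and a = 0.0975. Outcome risk is 0.00335/0.05163 = 6.5% in those classed as exposed and 0.03102/0.94837 = 3.3% in the rest, so RR = 1.98. The odds ratio, which is what a logistic model returns, is a(1 − b)/[b(1 − a)] = 2.05.

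The ends of the range, all at p = 5%, are:

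| Admission tests k | Other tests m | ICC | b | a | RR | OR |
|---|---|---|---|---|---|---|
| 1 | 2 | 0.7 | 0.0804 | 0.1027 | 1.30 | 1.31 |
| 1 | 1 | 0 | 0.0500 | 0.0975 | 1.98 | 2.05 |
| 3 | 2 | 0.7 | 0.0804 | 0.1350 | 1.74 | 1.78 |
| 3 | 1 | 0 | 0.0500 | 0.1855 | 3.94 | 4.33 |

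Results at p = 2% lie inside these ranges. The risk ratio should be 1.0. If r is set to 10% in the same formula, the ranges become 1.27-1.87 (k = 1) and 1.66-3.36 (k = 3).

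The calculation treats every outcome as an admission. Deaths without admission would dilute or reverse it. Admissions for other causes, which add tests to patients without the outcome, would narrow it.

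**Goal e under no true difference.** Here the ratio is simply that of the two case probabilities. For an assumed 6 versus 2 tests:

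- ICC 0: 0.1142/0.0396 = 2.88 at p = 2%, and 0.2649/0.0975 = 2.72 at p = 5%.
- ICC 0.7: 0.0677/0.0337 = 2.01 at p = 2%, and 0.1475/0.0804 = 1.84 at p = 5%.
- Equal numbers of tests: 1.00 whatever p and the ICC.

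**The case against.** **Goal e rests on an unstated premise.** The protocol nowhere says that patients with diabetes or renal failure are tested more often, and Section 1 names both as sources of real hyperkalaemia risk. This stands. A reader might infer that the any-value rule must make these groups look worse. The documents support only the conditional statement: plausible under usual-care testing, absent if testing is equal.

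**The direction is not uniform.** A reader might also infer that every association in goal d is pushed away from the null. That fails for death, which is also a separate outcome. A patient who dies early without admission never has the 12-month test, so has less chance of being classed as hyperkalaemic.

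**The size depends on assumptions.** Repeated potassium values in one patient are plausibly correlated, and patients without admission also have usual-care tests. Assuming independent tests and a single test in those patients gives only the upper end, so the ranges above relax both.

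**Section 3.7 already discloses it, and a SAP could deal with it.** Section 3.7 concedes that detection depends partly on admission. It presents this as missed mild episodes and does not say that the comparison with admission is distorted. Covariates and sensitivity analyses can be left to a SAP, and none was available here. But the case rule, the admission-linked test and the untimed logistic analysis are stated in the protocol, and following them as written gives a biased estimate.

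**Using only the 12-month value would be a poor cure.** This also stands. It would replace incidence during follow-up by point prevalence among survivors, with fewer cases.

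**Conclusion.** The point holds for goal d, for HF admission: under the stated rule the outcome generates exposure tests. With no true effect the apparent risk ratio is about 1.3-2.0 with one admission test and 1.7-3.9 with three. This assumes 1-2 other follow-up tests, 2-5% per test, ICC 0-0.7 and the outcome risk implied by Section 3.2. The direction for admission follows from the protocol's text; the size depends on those assumptions. For death without prior admission the bias may go the other way.

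Goal e is a conditional risk: a spurious ratio of 1.8-2.9 for an assumed 6 versus 2 tests, and 1.0 with equal testing. None of this shows that an observed association would be false. It shows that the analysis as written cannot separate true risk from detection.

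**What to change.** **Goal d.** Count as exposure only potassium values dated before the outcome event, and exclude those taken at or after the outcome admission. That rule alone would shorten the exposure window of patients with early events, while event-free patients keep theirs up to the 12-month test. So analyse hyperkalaemia as a time-dependent exposure, or use baseline hyperkalaemia or a landmark.

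**Goal e.** Keep the any-value incidence as the main analysis. Report the number of potassium tests per patient by group. Show the 12-month-visit value and the number of high values per test as sensitivity analyses. Do not rely on adjustment for the log number of tests, because a high value itself prompts repeat tests.

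**Data.** Confirm that the CRF (Appendix 1, not shown) records the date of every potassium test. The tests are already being reviewed, so any addition should be small.

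**Cost.** There is a little extra analysis, and goal d has fewer exposed patients. With baseline hyperkalaemia alone, the protocol's 10% prevalence gives about 0.10 × 600 = 60 exposed, against the 73 in Section 3.2. The 12-month sensitivity analysis has fewer cases and omits early deaths, so it belongs beside the main result and should not replace it.
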